13.3.5 Modified Unified Batten Disease Rating Scale Seizure Inventory (mUBDRS-Seizure)

The mUBDRS–Seizure inventory measures the type and frequency of seizures and the presence of seizure complications in CLN2 patients in the prior 3-month interval. The inventory is completed with the aid of caregiver/family member recall in the period between study visits.

This measurement is composed of 10 items as follows:

- Frequencies of primary generalized / atonic / myoclonic / complex partial / simple partial seizures (5 items)
- Presences of seizure complications (5 items): secondary generalization, absence, drops, Prolonged Post-ICTAL Period, and medication change/initiation

Each item of the frequencies is scored on a 4-point Likert scale: 0=“None in prior 3 months”, 1=“1-2 seizures in 3 months”, 2=“3-5 seizures in 3 months” and 3=“> 5 seizures in 3 months”.

Each item of the presences is scored on a 2-point Likert scale: 0=“None in prior 3 months” and 1=“Present in prior 3 months at least once”.

Total Score: This is the sum of all the items over the number of items answered on all the scales. If more than 50% of the items in the items are missing, the total scores should not be computed. Total score and change from baseline will be provided in a listing.

	BMN 190-203 Statistical Analysis Plan, Version 2.0	Pg. 36 of 53
---	---	--------------

13.3.6 Retinal Anatomy using Optical Coherence Tomography (OCT)

The retinal thickness parameters were assessed by Optical coherence tomography (OCT) for each eye:

- Central Foveal
- Central Retinal
- Retinal – 3mm nasal to the fovea
- Retinal – 3mm temporal to the fovea

Rate of decline in thickness will be computed for each eye and each parameter based on the baseline and last assessments, scaled in units of 24 weeks. Summaries will be for each of the eyes and the average of the eyes. Thickness parameters and change from baseline will be summarized by visit. Individual patient data on thickness parameters will be plotted. The overall OCT assessment (normal, abnormal) will be summarized by visit.

The Weill Cornell Ophthalmic Scale will be performed on the optic nerve, vasculature, macula, and periphery for each eye. The overall severity scale is based on both eyes and has values ranging from 1 to 5. Overall severity and change from baseline will be summarized by visit. Individual patient severity data will be plotted.

A listing which combines the thickness and overall assessment by OCT, and overall severity scale from Weil Cornell Ophthalmic Scale will be provided.

13.3.7 Ophthalmologic Assessment

The measurements and the overall comparison of ophthalmoscopy to most recent assessment will be provided in a listing.

13.3.8 Visual Acuity

All subjects undergo Preferential Looking Testing (PLT) every 12 weeks. In addition, for those children who retain the cognitive function to adhere to testing, the Lea Vision Test or E Hook (or Tumbling E) Vision Test are also performed during the same assessment.

The assessment of visual acuity will be provided in a listing.

13.3.9 CLN2 Scale Vision Score

The 0-3 point Vision score (V) will be summarized and interpolated similarly to the ML endpoint (Section 13.1.5).

	BMN 190-203 Statistical Analysis Plan, Version 2.0	Pg. 37 of 53
---	---	--------------

13.3.10 CLN2 Scale Seizure Score

The 0-3 point Seizure score (S) will be summarized and interpolated similarly to the ML endpoint (Section 13.1.5).

13.3.11 Anti-epileptic treatment

Graphical displays for each patient will include start and end dates for anti-epileptic treatment, with indication whether prophylactic or acute use. Convulsion adverse events per SMQ and the 0-3 point S score will also be plotted on the patient chart.

13.3.12 Infant Toddler Quality of Life Questionnaire (ITQOL)

The Infant Toddler Quality of Life Questionnaire (ITQOL) is to assess levels of health and wellbeing in children aged between 2 months to 5 years. This tool asks parents of pre-school children to reflect on physical and psychosocial domains for development, pain, moods, and impact of child health on parents, including overall health, physical abilities, overall growth and development, discomfort/pain, temperament and moods, general behavior, global behavior, getting along with others, general health perceptions, change in health, parent impact - emotional, parental impact - time, family cohesion,

The assessment of ITQOL has been terminated from the study (refer the protocol amendment dated on 17 December 2018). The transformed raw score for each domain, as well as change from baseline, will be provided in a listing.

13.3.13 EQ-5D-5L

The EQ-5D-5L instrument is a self-reported questionnaire designed to measure general health status (The EuroQol Group, 1990, Health Policy), (Brooks, 1996, Health Policy). The EQ-5D-5L is composed of 2 parts: a descriptive system that assesses 5 levels of perceived problems (mobility, self-care, usual activities, pain/discomfort, and anxiety/depression) in 5 dimensions and the EQ visual analogue scale (EQ VAS) assessment for overall health (1-100).

The assessment of EQ-5D-5L has been terminated from the study (refer the protocol amendment dated on 17 December 2018). The 5 levels of perceived problems will be provided in a listing. The EQ VAS and change from baseline will be provided in a listing as well.

13.3.14 CSF/ Blood Biomarkers

Samples of blood and CSF will be collected prior to infusion and may be used to evaluate biochemical, molecular, cellular, and genetic aspects relevant to CLN2 disease, and to develop the assays used for these evaluations.

BIOMARIN®	BMN 190-203 Statistical Analysis Plan, Version 2.0	Pg. 38 of 53
------------------	---	--------------

Analysis of disease-related biomarkers from CSF and blood will be conducted if the usable biomarkers have been identified.

13.3.15 Electroencephalograms (EEG)

A standard electroencephalogram (EEG) will be recorded with 48 hours before infusion. The EEG data will be listed.

13.4 Examination of Efficacy by Subgroups

Analyses for asymptomatic patients (ML < 6) is described in Section 13.2.1. The primary endpoint analyses will be performed on the baseline ML=6 and baseline ML < 6 subgroups (Section 13.1.2).

ML score and MRI parameters will be summarized by visit for the age groups <2, <3, and ≥ 3 years, similarly to the overall population analysis (Section 13.1.5 and Section 13.2.3).

	BMN 190-203 Statistical Analysis Plan, Version 2.0	Pg. 39 of 53
---	---	--------------

14 SAFETY EVALUATIONS

Safety will be assessed by examination of adverse events (including SAEs, hypersensitivity reactions, infusion-associated reactions, and adverse events of special interest), clinical laboratory results (including chemistry, hematology, urinalysis, and CSF), vital signs, ECGs, EEGs, and immunogenicity.

Safety variables will be summarized descriptively. No formal inference will be conducted. The summarization will be based on the safety analysis population.

14.1 Adverse Events

Adverse events will be coded in accordance with the most current version of MedDRA at the time of coding.

Only treatment-emergent adverse events (TEAEs) will be summarized. A TEAE is defined as any AE that newly appeared, increased in frequency, or worsened in severity following ICV surgery. If the onset date of an AE is missing or indeterminate, the AE will be considered treatment emergent.

14.1.1 All Adverse Events

The incidence and number of events for all TEAEs will be summarized by system organ class (SOC), preferred term (PT) and severity (CTCAE grade). For AEs that occurred more than once during the study, the maximum severity will be used.

Adverse events that did not resolve or resolved with sequelae will be listed.

14.1.2 Drug-Related Adverse Events

All TEAEs assessed by investigator as study drug related will be summarized by SOC, PT and severity.

14.1.3 Deaths and Serious Adverse Events

Serious adverse events (SAEs) will be summarized in a similar manner to general adverse events. A listing of AEs for subjects who died and a listing of all SAEs will be provided.

14.1.4 Adverse Events Causing Premature Discontinuation

Adverse events that caused premature discontinuation of study or study drug will be listed.

	BMN 190-203 Statistical Analysis Plan, Version 2.0	Pg. 40 of 53
---	---	--------------

14.1.5 Convulsion Events

Convulsion events are adverse events that map to the broad Convulsions Standardized MedDRA Query (SMQ). Convulsion events will be summarized by SOC, PT and severity. The convolution events will also be summarized by 24-week study intervals: 0-24 weeks, 24-48 weeks, etc. The analyses will be repeated for subgroups ML=6 and ML<6 at baseline (pre-symptomatic and symptomatic) separately.

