4 LIST OF ABBREVIATIONS AND DEFINITIONS OF TERMS

AE	adverse event
AEoSI	adverse event of special interest
BPV	BioMarin Pharmacovigilance
CBC	complete blood count
CFR	Code of Federal Regulations
CLN2	neuronal ceroid lipofuscinosis type 2 disease, also known as classical late infantile CLN2, cLINCL, or Jansky-Bielschowsky disease, a form of Batten Disease
CNS	central nervous system
CRA	clinical research associate
CSF	cerebrospinal fluid
СТ	computed tomography
CTCAE	Common Terminology Criteria for Adverse Events
DRB	Data Review Board
ECG	electrocardiogram
eCRF	electronic case report form
EDC	electronic data capture
EEG	electroencephalogram
ERT	enzyme replacement therapy
EudraCT	European Union Drug Regulating Authorities Clinical Trials
FDA	Food and Drug Administration
GCP	Good Clinical Practice
HIPAA	Health Insurance Portability and Accountability Act
IB	investigator brochure
ICF	informed consent form
ICH	International Conference on Harmonisation of Technical Requirements for Registration of Pharmaceuticals for Human Use
ICH E6	ICH Harmonised Tripartite Guideline: Guideline for Good Clinical Practice E6
ICV	intracerebroventricular
IEC	Independent Ethics Committee
IND	Investigational New Drug (application)
IRB	Institutional Review Board
IT-L	intrathecal lumbar
ITQOL	Infant Toddler Quality of Life Questionnaire
MedDRA	Medical Dictionary for Regulatory Activities
ML	Combined score of motor and language subscales on the adapted CLN2 disease rating scale
MRI	magnetic resonance imaging
mUBDRS- Movement	Modified Unified Batten Disease Rating Scale Involuntary Movement Scale

BOMARIN[®] 190-203 Amendment 6

mUBDRS- Seizure	Modified Unified Batten Disease Rating Scale Seizure Inventory
NAb	neutralizing anti-TPP1 antibody
NCI	National Cancer Institute
NOAEL	No-observed-adverse-effect-level
OCT	Optical Coherence Tomography
PEDsQL	Pediatric Quality of Life
PEG	percutaneous endoscopic gastrostomy
PLT	Preferential Looking Test
РК	pharmacokinetics
QOL	quality of life
REC	Research Ethics Committee
SAE	serious adverse event
SAP	statistical analysis plan
SDV	source data verified
SOI	Statement of Investigator
SUSAR	suspected unexpected serious adverse reaction
TAb	total anti-TPP1 antibody
TRE	temporally related events
TPP1	tripeptidyl peptidase-1
UBDRS	Unified Batten Disease Rating Scale
US	United States

Page 19

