7 INTRODUCTION

CLN2 disease is a predominantly late infantile form of neuronal ceroid lipofuscinosis and one of the multiple genetic isoforms of Batten Disease. CLN2 is a very rare genetic disease characterized by the deficiency of the lysosomal serine protease TPP1, caused by mutations in the *CLN2* gene. In the absence of TPP1, lysosomal storage materials normally metabolized by this enzyme accumulate as characteristic intracellular deposits in many organs; accumulation in the CNS leads to the neurodegenerative symptoms and, ultimately death. The onset of symptoms is typically between ages 2 and 4 (Chang, 2011); (Kurachi, 2000) with an average age of diagnosis of 4 years (Worgall, 2007). Patients typically present initially with seizures, followed by ataxia, myoclonus, impaired speech, cognitive decline, and developmental regression. A loss of vision follows psychomotor decline, with patients blind and non-ambulatory typically between 6 and 8 years of age. Patients enter into essentially a neurovegetative state during the later stages of the disease and feeding and tending to everyday needs become difficult. Disease progression is rapid with death typically occurring between 10 and 15 years of age.

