4.6 Handling of Dropouts and Missing Data

Missing ML assessments for symptomatic patients (baseline ML < 6 points) will not have much impact on the assessment of the primary endpoint since the disease progression on ML score is close to linear, estimation of rate of decline in ML is reliable for follow-up periods of greater than 6 months and all subjects had been followed > 6 months. Impact of missing ML assessments for asymptomatic subjects (baseline ML = 6 points) is also expected to be low since the follow-up of matched Study 190-901 subjects is limited to the length of follow-up of the Study 190-203 subject matched. Additional analyses will be conducted as appropriate to evaluate the impact of the COVID-19 pandemic on the study conduct and results, especially for the treatment effect as estimated in the trial.

BIOMARIN®	BMN 190-203 Statistical Analysis Plan, Version 2.0	Pg. 17 of 53
------------------	---	--------------

Statistical models for time-to-event analyses accommodate variable follow-up arising from staggered accrual or early study discontinuation, using an assumption of missing at random.

The CLN2 assessment schedule for Study 190-901 is not regular and does not generally match CLN2 assessment frequency in Study 190-203. Summaries of CLN2 score over a window grid would have highly variable N which is difficult to interpret. For this reason, interpolation will be used. Summaries of matched Study 190-203 and Study 190-901 CLN2 data will be based on data that has been imputed to the Study 203 visit target, using linear interpolation between Study 190-901 subject visits. Details are provided in [Appendix 4](#).

Partial or missing dates for adverse events and medications will be imputed conservatively by assignment to the earliest and latest possible dates for start and stop dates, respectively.

Some patients only have year of birth recorded as permitted by the site Institutional Review Board. Age in integer months is provided at each visit for Denver assessment. For subjects with incomplete date of birth provided, the date of birth will be imputed by back-calculation of birth date from the date of Denver assessment: (date of Denver) – round ((age in months) x (365.25/12)). For subjects with multiple Denver assessments, the average of the imputed date of births is used.

BIOMARIN®	BMN 190-203 Statistical Analysis Plan, Version 2.0	Pg. 18 of 53
------------------	---	--------------

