13.2 Secondary Efficacy Endpoint(s)

13.2.1 Time to Disease Manifestation

For analysis purposes, asymptomatic patients are defined as the patients with baseline MLVS = 12. Subsequent disease manifestation is defined as post-baseline consecutive measurements of M, L, V, or S scores that are less than 3 and at least 22 days apart. The time of disease manifestation is defined as the time of the first of the two measurements demonstrating the deficit. Kaplan-Meir analysis will be performed.

For patients who have not presented with CLN2 disease symptoms prior to initiation of treatment (baseline), onset of disease symptoms captured in AE reporting will be described.

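### The convulsion tables call children with baseline ML = 6 pre-symptomatic, although ML has no seizure item, so first-ever and worsening seizures are mixed under that label

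*SAP*

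**What the plan says.** SAP 14.1.5 takes convulsion events from the broad Convulsions SMQ, summarises them by system organ class, preferred term, severity and 24-week interval, and repeats this for "subgroups ML=6 and ML<6 at baseline (pre-symptomatic and symptomatic) separately".

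The protocol's abbreviation list defines ML as "Combined score of motor and language subscales on the adapted CLN2 disease rating scale". Protocol Section 7 gives the usual order of symptoms: "Patients typically present initially with seizures, followed by ataxia, myoclonus, impaired speech, cognitive decline, and developmental regression".

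SAP Version 2.0 describes children without symptoms in three other places:

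- Section 13.2.1, for time to disease manifestation: "asymptomatic patients are defined as the patients with baseline MLVS = 12". Manifestation is then a confirmed M, L, V or S score below 3.
- Section 4.6, on missing data: "Impact of missing ML assessments for asymptomatic subjects (baseline ML = 6 points) is also expected to be low".
- Section 13.4, on subgroups: "Analyses for asymptomatic patients (ML < 6) is described in Section 13.2.1".

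Two further rules decide what reaches the tables. SAP 14.1 counts as treatment-emergent any event that is new, more frequent or more severe after ICV surgery. Protocol 10.3.1.6 exempts seizures unchanged from baseline from AE reporting, but requires new-onset, worsened and new-type seizures to be reported.

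**The concern.** The tables concern seizures, but the variable that splits them carries no information about seizures. A child with normal gait and language and established epilepsy has ML = 6 and is placed in the pre-symptomatic column. If that child's seizures worsen or change type, the event appears there beside a first-ever seizure in a previously unaffected child.

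Protocol 7.2 lists convulsions among the common AEs of this product, and the study deliberately enrols young and mildly affected children. A reader of the final report will naturally take the pre-symptomatic column as the rate at which seizure-free children develop convulsions on treatment. The table does not measure that.

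**Working it through.** The plan states no figure on this point, so there is none to reproduce. The check compares the definitions and traces which events enter the table.

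**Inputs.** Protocol Appendix 1 scores motor (M), language (L), vision (V) and seizures (S) from 0 to 3 each. S refers to grand mal seizures, and S = 3 means none in a 12-week period. ML = M + L; MLVS = M + L + V + S.

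**Step 1: count the possible baseline patterns.** In total there are 4 × 4 × 4 × 4 = 256.

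| Place in SAP | Rule | Patterns |
|---|---|---|
| 14.1.5 (pre-symptomatic) and 4.6 (asymptomatic) | ML = 6, so M = L = 3 with V and S free | 4 × 4 = 16 |
| 13.2.1 (asymptomatic) | MLVS = 12 | 1 |
| 13.4 (asymptomatic, as printed) | ML < 6 | 256 − 16 = 240 |

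The MLVS = 12 pattern is one of the 16 with ML = 6, so those two rules are nested. ML < 6 shares no pattern with either.

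**Step 2: seizure deficits within ML = 6.** V takes any of 4 values and S any of 3 values below 3, giving 4 × 3 = 12 of the 16 patterns. For each of these MLVS is at most 3 + 3 + 3 + 2 = 11, so 13.2.1 does not count the child as asymptomatic while 14.1.5 calls the child pre-symptomatic. These are possible scores, not children.

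**Step 3: which events enter the table.**

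- Unchanged baseline seizures are generally not AEs, so epilepsy alone does not put a child in the numerator.
- Worsened and new-type seizures are AEs, and SAP 14.1 pools them with new ones.
- Seizures within 24 hours of infusion start are to be reported as events of special interest, with the investigator noting whether they fit baseline activity. SAP 14.1.5 does not say how that note is used.

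**Step 4: possible size.** Let n be the number of ML = 6 children and j the number of them with prior seizures and a reportable convulsion event. With no first-ever seizure at all, the column reads j/n. Neither number is in the documents; SAP Appendix 3 gives only a potential 14 matched pairs. Assuming n = 8, each such child adds 1/8 = 12.5 percentage points, and the column could read anything from 0/8 = 0% to 8/8 = 100%. This shows sensitivity to single children; it is not an estimate.

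**Step 5: would MLVS = 12 repair the split?** Only partly. S = 3 looks back 12 weeks and covers grand mal seizures, so a child with earlier or other types of seizure can still have MLVS = 12. The remaining group would also combine children with epilepsy and seizure-free children who have a motor, language or vision deficit.

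**The case against.** A reader might infer that new-onset convulsions cannot be separated from existing epilepsy at all. The documents do not support that:

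- Protocol 10.3.1.6 keeps most unchanged seizures out of the AE data and lists new-onset, worsened and new-type seizures as separate reporting situations.
- SAP 13.3.11 plots convulsion AEs, the S score and anti-epileptic treatment for each patient.
- SAP 13.2.1 describes symptom onset from AE reports in children without symptoms before treatment.
- SAP 8 summarises the baseline S score, and 13.3.5 lists the mUBDRS-Seizure total score.

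This stands, and it limits the point to what the subgroup tables show. It does not remove it. Charts, listings and narratives give no incidence, and the 13.2.1 Kaplan-Meier analysis pools motor, language, vision and seizure deficits.

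A reader might also infer three incompatible definitions of asymptomatic. That is too strong. Section 13.2.1 is the only formal definition, 4.6 is a remark in a missing-data rationale, and ML = 6 contains MLVS = 12. The parenthesis in 13.4 points to 13.2.1 and is absent from the corresponding section of the June 2020 SAP, so it looks like a slip. It is still wrong as printed.

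Finally, 14.1.5 states its cut explicitly, the cut matches the efficacy subgroups in 13.1.2, and Protocol 9.2 calls motor and language the earliest domains to lose function. This supports ML as a measure of progression and as a secondary split. It does not make ML a measure of seizure status, and Protocol Section 7 puts seizures first among presenting symptoms.

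**Conclusion.** The point holds for the planned tables. SAP 14.1.5 attaches a pre-symptomatic label to a group defined without reference to seizures. Its ML = 6 column would combine first-ever convulsions with worsening or new-type seizures in children who already have epilepsy. Under the SAP's own 13.2.1 rule, any ML = 6 child with S below 3 is already symptomatic.

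The size in children is unknown and could be zero: it depends on how many ML = 6 children had prior seizures and then had a reportable event. The consequence is limited to descriptive safety summaries, for which SAP Section 14 plans no formal inference. The primary analysis is not affected: its ML = 6 and ML < 6 subgroup repeats use the score cut and do not depend on the label.

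**What to change.** - **SAP 14.1.5:** summarise convulsion events by seizure history before the first infusion, none versus any. Take this from the seizure history collected at Screening (Protocol 12.1), supported by the Baseline S score and mUBDRS-Seizure (Protocol 12.3.1). Do not use MLVS = 12 alone, for the reason in the last step of the check.
- **Same section:** if the ML = 6 and ML < 6 split is wanted for alignment with the efficacy subgroups, keep it as a secondary table without the pre-symptomatic and symptomatic labels.
- **SAP 13.4:** change the parenthesis from ML < 6 to MLVS = 12, to agree with 13.2.1.
- **SAP 4.6:** describe the group as children with baseline ML = 6 and drop the word asymptomatic.

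The cost is one derived flag, a few words and one more table. All the data are already collected. The small downside is that the new subgroups will contain few children, so counts should be shown beside any percentages.

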14.1.6 Hypersensitivity Adverse Events

A hypersensitivity adverse event (HAE) is defined as any adverse event that maps into either:

- the broad “hypersensitivity” Standardized MedDRA query (SMQ), or
- the broad algorithmic “anaphylactic reaction” SMQ

Note: The algorithm requires either one or more of the following: an “A” event, or “B & C” events, or “B & D” events, or “C & D” events, with onset within 24 hours of start of a study drug infusion.

HAEs will be summarized in a similar manner to general adverse events.

